In PsA Phase 2 study [CLR\_16\_23 PsA study], both tildrakizumab, 200 mg q12 weeks and tildrakizumab 100 mg, q12 weeks provided similar efficacies in the ACR20, ACR50, and ACR70 at Week 24. The lowest dose of 20 mg q12 weeks, did not demonstrate superiority over placebo in ACR70 and had numerically lowest ACR 50 response among the active doses tested. The highest dose of tildrakizumab 200 mg q4 weeks, did not provide significant benefit over tildrakizumab 200 mg, q12 weeks. Therefore, the dose regimen of tildrakizumab 100 mg, q12 weeks is chosen for the long-term extension study going forward.

Subjects not deriving sufficient clinical benefit in the opinion of the Investigator at any time after the initiation of this long-term extension study should be discontinued from IMP as described in [Section 9.3.5](#), and receive clinical care as determined by the Investigator.

With the exception of those who withdraw informed consent, subjects who withdraw from IMP during the long-term extension study, will undergo the EoT assessments approximately

4 weeks after their last administration of IMP. Subjects who complete treatment to Week 200 will return for a Follow-up assessment at Week 208 (4 years).

The primary safety objectives of this study include assessment of the long-term safety of tildrakizumab by evaluation of incidence and intensity of AEs, and changes in vital signs, laboratory assessments, ECGs, C-SSRS, and immunogenicity data.

No independent assessor is needed to assess efficacy measurements. There will be no efficacy assessments during the LTE study. The Principal Investigator (PI)/designee will be responsible for performing safety evaluations.

Clinical Adjudication Committee (CAC) will be established to evaluate cardiovascular events ([Section 13.3.6](#)).

End of study is defined as the last visit of the 4-year treatment period (Week 208, EoT/Follow-up) for the last global subject.

This study will be conducted in compliance with the protocol and with the International Council for Harmonisation (ICH) of Technical Requirements for Pharmaceuticals for Human Use guidelines on Good Clinical Practice (GCP).

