**Table 9-1 Schedule of Assessments for PsA Subjects**

Visit a	1	2	3	4	5	6	7	8	9	10	11	12	13	14	15	16	17	18	19	EoT/ FU
Week (± 7D)	0 b	8	20	32	44	56	68	80	92	104	116	128	140	152	164	176	188	200	208 c	
Written informed consent	X																			
Inclusion/Exclusion criteria	X																			
Demographic information d	X																			
Physical examination	X					X				X					X			X	X	
Vital signs	X	X	X	X	X	X	X	X	X		X		X		X	X		X	X	
AEs/Concomitant medications e	X	X	X	X	X	X	X	X	X	X	X	X	X	X	X	X	X	X	X	
Medical/Medication history e	X																			
ECG	X					X				X					X				X	
IMP administration f	X	X	X	X	X	X	X	X	X	X	X	X	X	X	X	X	X	X		
Hematology/chemistry/urinalysis g	X		X			X				X					X			X	X	
Lipids h	X		X			X				X					X			X	X	
Urine pregnancy test i	X	X	X	X	X	X	X	X	X	X		X		X		X		X	X	
hsCRP and ESR i	X		X			X				X				X				X	X	
Anti-drug antibodies	X		X			X				X				X				X	X j	
PK sample h	X		X			X				X				X				X	X	
C-SSRS k	X	X	X	X	X	X	X	X	X	X	X	X	X	X	X	X	X	X	X	

Abbreviations: AE = adverse event; BL = Baseline; C-SSRS = Columbia-Suicide Severity Rating Scale; D = days; ECG = electrocardiogram; ESR = erythrocyte sedimentation rate; EoT = End of Treatment; FU = Follow-up; hsCRP = high sensitivity C-reactive protein; IMP = investigational medicinal product; M = months; PK = pharmacokinetic; PsA = psoriatic arthritis; W = weeks; Y = year(s).

- a Visits will be scheduled every 12 weeks in the first two years, followed by every 24 weeks in the last two years. Collection of AEs and concomitant medications, as well as any unscheduled safety assessment deemed appropriate in the opinion of the Investigator to ensure subject safety, will be performed at each visit. In addition, following completion and database lock of the parent PsA Phase 2 study, the long-term extension study will have the option to become open-label for these subjects.
- b The BL visit of the study Visit 1 (Week 0, Day 1) will be the same as Visit 16, Week 52 of parent PsA study (or later for subjects who entered the wash-out phase from the parent study due to the timing of study site activation of the long-term extension study).
- c Subjects who withdraw from IMP at any time will complete the EoT/FU assessments approximately 4 weeks after administration of the last dose of IMP.

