### **9.3.6 Lost to Follow-Up**

All reasonable efforts must be made to locate subjects to determine and report their ongoing status. This includes follow-up with persons authorized by the subject. Lost to follow-up is defined by the inability to reach the subject after a minimum of 3 documented phone calls, faxes or emails (not performed on the same day), as well as a lack of response by the subject to a registered mail letter. All attempts should be documented in the subject's medical records. If it is determined that the subject has died, the study site will use permissible local methods to obtain the date and cause of death and as much other information as can be obtained, including post mortem reports.

Data to be collected at subsequent visits will be considered missing.

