#### **11.1.1.8 Recording of Adverse Events**

Any relevant observations made before the end of the Baseline visit (prior to signing the ICF for this long-term extension study) are to be recorded on the AE eCRF, but will not be considered TEAEs and will be reported separately from TEAEs. Any relevant observations

made after signing the ICF will be recorded as an AE in the subject's AE eCRF (see [Section 11.1.1.1](#)).

For the purposes of this study, any detrimental change in the subject's condition, after the first dose of IMP for the long-term extension study and up to completion of the EoT/Follow-up visit, should be considered an AE.

The following variables will be recorded for each AE: verbatim/AE description and date for AE start and stop, intensity, seriousness, causality rating, whether or not the AE caused the subject to discontinue, and the outcome. A new AE must be recorded if the intensity of the AE changes.

All AEs/SAEs have to be reported to the Sponsor, whether or not considered causally related to the IMP or to the study procedure(s).

All ongoing AEs/SAEs should be followed up until resolution or stabilization or the last visit if in the Investigator's opinion, the AE is unlikely to resolve due to the subject's underlying disease.

At any time after the subject has taken the first dose of IMP, if an Investigator learns of an SAE that can be reasonably related to IMP, he/she should promptly notify the Sponsor.

The Investigator will assess the intensity of AEs based on the following definitions:

- Mild (awareness of sign or symptom, but easily tolerated),
- Moderate (discomfort sufficient to cause interference with normal activities),
- Severe (incapacitating, with inability to perform normal activities).

It is important to distinguish between serious and severe AEs. Severity is a measure of intensity whereas seriousness is defined by the criteria in [Section 11.1.1.2](#).

An AE of severe intensity need not necessarily be considered serious. For example, nausea that persists for several hours may be considered severe nausea, but not an SAE. On the other hand, a stroke that results in only a limited degree of disability may be considered a mild stroke but would be an SAE.

For an AE to be a suspected drug-related event, there should be at least a reasonable possibility of a causal relationship between the IMP and the AE.

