## 8.5 Extent of exposure

### 8.5.1 Treatment Duration

Duration of study drug exposure (in days) will be calculated as: last dose date – first dose date + 1 day, regardless of study drug interruption.

Study drug exposure will be summarised by treatment group using descriptive statistics.

Exposure to randomized study drug will also be categorised in intervals  $\leq 3$  months ( $<91$  days), 3-6 months (91-180 days), 6-12 months (181-365 days), 1-2 years (366-730 days), 2-3 years (731-1095 days),  $>3$  years ( $>1095$  days) and summarized by treatment group.

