### 8.7.1 Adverse events

Any AE that started in the parent study must be reported on the medical history form in this extension study. Only those events that start on/after enrollment into the extension study or are ongoing at the start of the extension study and become worse after or concurrently to extension study enrollment must be reported as AEs.

All AEs will be classified by Primary System Organ Class (SOC) and Preferred Term (PT) according to the most recently available version of the MedDRA dictionary.

In summaries by SOC and PT, adverse events will be sorted within each SOC and PT in alphabetical order. In summaries by PT, AEs will be sorted within each PT in alphabetical order.

Details for imputing missing or partial start dates of adverse events are described in [Section 7.2.2](#).

TEAEs are defined as any AEs occurring or worsening on or after the date of signing of the Informed Consent Form for the extension study. AE summary tables will be presented for TEAEs only and will include the following:

- All TEAEs
- Related TEAEs (AE will be defined as related if causality is possibly, probably, or certainly related)
- TEAEs by maximum severity

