# Statistical Analysis Plan (SAP)

- TEAEs leading to study discontinuation
- Serious TEAEs
- TEAEs leading to death.

An overall summary for the categories above will be presented by treatment group and overall.

Due to the various durations of exposure to a treatment, the exposure-adjusted AE incidence rate (per 100 subject-years) will be summarized by treatment group. The incidence of AEs will be presented by system organ class and PT. In addition, all TEAEs will be summarized by SOC, PT and treatment group using frequency counts and percentages (i.e., number and percentage of subjects with an event).

Where a subject has the same adverse event, based on preferred terminology, reported multiple times in the study, the subject will only be counted once at the preferred terminology level in adverse event frequency tables.

Where a subject has multiple adverse events within the same system organ class in the study, the subject will only be counted once at the system organ class level in adverse event frequency tables.

When reporting adverse events by intensity, in addition to providing a summary table based on the event selection criteria detailed above, summary table will also be provided based on the most intense event - independent of relationship to study treatment.

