# Statistical Analysis Plan (SAP)

laboratory results is to be reported as a non-serious AECI, using the terminology "accidental or intentional overdose without adverse effect."

2. An elevated AST or ALT laboratory value that is  $\geq 3 \times$  the ULN and an elevated total bilirubin laboratory value that is  $\geq 2 \times$  ULN and, at the same time, an alkaline phosphatase laboratory value that is  $< 2 \times$  ULN, as determined by way of protocol-specified laboratory testing or unscheduled laboratory testing, is to be reported as a non-serious AECI.
3. Infections that require IV antibiotics but do not meet the definition of an SAE will be designated a closely monitored AE for this study.
4. Depression and suicidal ideation and behavior events.

In addition, a listing containing individual subject adverse event data for TEAEs leading to discontinuation from study, Serious TEAEs, TEAEs leading to death, AESIs, and ECIs will be provided separately. All AEs, including pre- and post-treatment AEs, will be presented in an individual subject data listing.

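### SAP 7.2.2 moves partial AE start dates known to precede the first dose up to that dose, so a pre-consent event on the AE form can become a TEAE; the AE rate's person-time also needs stating

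*SAP*

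**What the plan says.** **Dates.** SAP 7.2.2 imputes a partial AE start date as the first of the known month, or as 1 January when only the year is known. If the result is earlier than the first dose date, that date replaces it. If the result is later than the stop date, the stop date replaces it. A completely missing start date becomes the first dose date, and no stop-date check is written for that case. The section does not say whether the parent or the extension first dose is meant, although SAP 7.1 separates the two.

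**TEAE definition.** SAP 8.7.1: "TEAEs are defined as any AEs occurring or worsening on or after the date of signing of the Informed Consent Form for the extension study". No end is given.

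**Recording of pre-consent events.** Protocol 11.1.1.1 and 11.1.1.8 put observations made before the extension consent on the AE eCRF and say they are not TEAEs. Protocol Table 9-1 footnote e, protocol 9.1.3.1.1 and the opening of SAP 8.7.1 send earlier or ongoing events to medical history. SAP 8.7.1 also says: "All AEs, including pre- and post-treatment AEs, will be presented in an individual subject data listing". It defines neither kind.

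**Rates.** In SAP 8.7.1, "the exposure-adjusted AE incidence rate (per 100 subject-years) will be summarized by treatment group". The only duration the SAP defines is in 8.5.1: last dose date minus "first dose date + 1 day, regardless of study drug interruption". Protocol 11.1.1.8 runs longer: a detrimental change "after the first dose of IMP for the long-term extension study and up to completion of the EoT/Follow-up visit, should be considered an AE". Completers have their last dose at Week 200 and their last visit at Week 208. Subjects who withdraw from IMP "will complete the EoT/FU assessments approximately 4 weeks after administration of the last dose of IMP". Protocol 11.1.2 collects SAEs for a further 30 days, and after that records fatal, drug-related or AESI SAEs without a stated limit.

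**The concern.** The incidence and intensity of AEs is the first primary objective, and nearly all AE tables are restricted to TEAEs. A date rule that overrides what is known about onset therefore affects the counts, the percentages and the rates. Flooring to the first dose is a sensible conservative choice when onset is ambiguous. Here it also applies when onset is not ambiguous, because the recorded month or year already places the event before treatment.

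The rate is the SAP's stated adjustment for unequal exposure. If its numerator runs to the follow-up visit or beyond while its denominator stops at the last dose, late events enter without their time. Two programmers could also obtain different rates from the same SAP, because it does not say whether a subject's time stops at the first event.

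**Working it through.** **1. Date rule on example dates.** The documents give no worked case. Take extension consent and first extension dose both on 12 June 2019 and, for comparison, a parent first dose 52 weeks earlier (13 June 2018). None of the events has worsened.

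| Recorded start | Stop | First dose = extension | First dose = parent |
|---|---|---|---|
| March 2019 | ongoing | 12 June 2019, TEAE | 1 March 2019, not TEAE |
| 2018 only | ongoing | 12 June 2019, TEAE | 13 June 2018, not TEAE |
| March 2019 | 1 July 2019 | 12 June 2019, TEAE | 1 March 2019, not TEAE |
| March 2019 | 20 May 2019 | 20 May 2019 (capped), not TEAE | 1 March 2019, not TEAE |
| June 2019 | ongoing | 12 June 2019, TEAE | 1 June 2019, not TEAE |
| missing | 20 May 2019 | 12 June 2019, after its own stop | not needed here |

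Under the extension reading, the first three rows are misclassified. The fourth shows that the cap protects partial dates of events that ended before the first dose, if it is applied after the floor. The last shows that the protection is not written for missing starts. Under the parent reading the misclassification goes away, but the fifth row shows that an event which may have begun after consent drops out. The SAP must name the dose in either case.

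**2. Person-time for a completer.** Exposure under SAP 8.5.1: X = 200×7 + 1 = 1401 days. Time to Week 208: W = 208×7 + 1 = 1457 days. W/X = 1.040, so AEs counted to Week 208 over X give a rate 4.0% higher than over W. For SAEs to 30 days later, 1487/1401 = 1.061.

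**3. Person-time for a cohort.** Assumptions: 286 subjects, exponential dropout at 0.05 or 0.30 per year, doses at Weeks 0, 8, 20, ..., 200, consent on the day of first dose. The inflation is E[W]/E[X]. Three cases cover withdrawals, because protocol 9.1.1 carves out some subjects ("With the exception of those who withdraw informed consent, subjects who withdraw from IMP") and protocol 9.3.6 says of those lost: "Data to be collected at subsequent visits will be considered missing".

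| Dropout per year | Subject-years to last dose | No EoT visit | EoT at 28 days | Later of 28 days or dropout |
|---|---|---|---|---|
| 0.05 | 992.7 | 1028.9 (+3.6%) | 1032.8 (+4.0%) | 1035.2 (+4.3%) |
| 0.30 | 630.5 | 644.4 (+2.2%) | 659.4 (+4.6%) | 668.8 (+6.1%) |

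The SAP describes 4-weekly injections, active or dummy, during blinded treatment. If these count as doses, the top figure falls to about +5.5% (4-weekly to Week 56) or about +4.5% (4-weekly throughout).

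**4. Against sampling error.** Exact Poisson 95% limits divided by the estimate are 0.48 to 1.84 for 10 events and 0.87 to 1.15 for 207 events. These counts are roughly 1 and 20 per 100 subject-years over 1,033 subject-years.

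**5. First-event convention.** Counting each subject once over full time, relative to stopping time at the first event, changes the rate by E[1 − exp(−rW)]/(r·E[W]) − 1. In the 28-day case, at dropout 0.05 and 0.30, this is −1.9% and −1.6% at an assumed true rate of 1 per 100 subject-years, −9.0% and −7.6% at 5, and −30.2% and −25.7% at 20.

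**The case against.** The strongest reply is that the misclassified events should not be on the AE form. SAP 8.7.1, Table 9-1 footnote e and protocol 9.1.3.1.1 send events that began earlier to medical history. Under SAP 8.7.1 such an event is reported as an AE only if it worsened, and then it is a TEAE by definition, so the floor classifies it correctly. This stands as a limit on the point. It does not remove it, because protocol 11.1.1.1 and 11.1.1.8 direct pre-consent observations to the AE eCRF and the SAP itself expects pre-treatment AEs in its AE listing.

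On the rate, the reply is that the effect is small, no tests are planned, percentage tables do not use the denominator, the protocol bounds most AE collection, and SAP section 9 places table templates in a separate document that may define the rate. The SAP also already states once-per-subject counting for its frequency tables. All of this stands, and it is why the rate is a secondary clarification.

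A reader might infer that TEAE counts will be substantially inflated, or that rates will favour one regimen. The documents support neither. The number of affected events depends on recording practice and on how many start dates are partial. The direction of any between-group difference would depend on dropout and follow-up by group, which are unknown.

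**Conclusion.** The date rule is wrong as written, on two conditions: the first dose is the first extension dose, and the pre-consent event is on the AE eCRF and is either ongoing or ended on or after that dose. The missing stop-date cap for completely missing starts is a separate defect under the extension-dose reading. Neither is quantified.

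The rate is under-specified rather than wrong. If SAP 8.5.1 supplies the denominator, inflation is +4.0% for a completer and about +2% to +6% for a cohort under the assumed dropout and the 12-weekly grid, with the top nearer 4.5% to 5.5% if blinded 4-weekly injections count. For common events the unstated first-event rule moves the rate more than the window does. One might read the SAP's open-ended TEAE definition as meaning that AEs are gathered indefinitely. The protocol does not support that: only late fatal, drug-related or AESI SAEs have no limit. Confidence is moderate.

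**What to change.** 1. **SAP 7.2.2.** Name the first extension dose. Apply the floor only when the known month and year (or the year, if only that is known) are those of this dose. Leave earlier dates as pre-treatment, unless the record is a worsening or the known month is that of an earlier extension consent. Apply the stop-date cap to completely missing starts.
2. **Recording.** Reconcile protocol 11.1.1.1 and 11.1.1.8 with Table 9-1 footnote e, protocol 9.1.3.1.1 and SAP 8.7.1 on where pre-consent events go.
3. **SAP 8.7.1.** Keep the start at extension consent. State one end, either EoT/Follow-up or last dose plus a stated period, or last contact or data cut-off if earlier. Use the same window for events and subject-years. State the once-per-subject-per-PT numerator and whether time stops at the first event. Define post-treatment AE, and tabulate separately all SAEs recorded after the window, not only deaths and AESIs. Keep 8.5.1 for the drug-exposure table.

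The cost is some SAP wording and derivation code, plus one protocol clarification. Late events leave the main TEAE tables for a separate display. Identifying worsening may need data review: the AE variables listed in protocol 11.1.1.8 include no worsening flag, and a new record is required only when intensity changes, whereas 11.1.1.1 also counts worsening in nature or frequency.

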## **8 STUDY OBJECTIVES**

### **8.1 Primary Safety Objectives**

To assess the long-term safety of tildrakizumab when administered to PsA subjects by evaluation of:

- Incidence and intensity of all AEs,
- Changes in vital signs, laboratory assessments, electrocardiograms (ECGs), and Columbia-Suicide Severity Rating Scale (C-SSRS),
- Immunogenicity of multiple-dose administration of tildrakizumab in these subjects.

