### **9.3 Selection of Study Population**

#### **9.3.1 Inclusion Criteria**

Subjects may be included in the study if they meet all of the following criteria:

1. Subject has provided written informed consent for this long-term extension study.
2. Subjects with PsA who met the inclusion criteria of the parent study and completed the parent study treatment period (e.g., up to Week 48 for the parent Phase 2 study, with return for the EoT assessment at Week 52).
3. PsA subjects who achieved a 20% reduction from Baseline in American College of Rheumatology (ACR)20 response criteria at Week 52 (for details see [Appendix 22.2](#)), AND the subject has received sufficient clinical benefit, in the opinion of the Investigator, to support continued treatment with tildrakizumab.

Note: This criterion using response criteria at Week 52 of the parent study will apply to all subjects, including those subjects who enter the study from the wash-out phase of their parent study (after Week 52) due to the timing of study site activation of the long-term extension study.

4. No concomitant use of both leflunomide and methotrexate,
5. No history of active tuberculosis (TB) or symptoms of TB.

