9. Subject has any concurrent medical condition or uncontrolled, clinically significant systemic disease (e.g., renal failure, heart failure, hypertension, liver disease, diabetes, or anemia) that, in the opinion of the Investigator, could cause continued treatment to be detrimental to the subject.
10. Subject has a known history of infection with hepatitis B, hepatitis C, or human immunodeficiency virus during the parent study.
11. Subject had myocardial infarction, unstable angina pectoris, or ischemic stroke within the past 6 months prior to the first IMP dose for this extension study.
12. Subject has any active malignancy, including evidence of cutaneous basal or squamous cell carcinoma or melanoma.
13. Subject has a history of malignancy EXCEPT treated and considered cured cutaneous basal or squamous cell carcinoma, *in situ* cervical carcinoma, OR *in situ* breast ductal carcinoma.
14. Subjects with a history of alcohol or drug abuse during the parent study.
15. Significant risk of suicidality at the Baseline assessment ([Section 9.1.1](#)) of this extension study based on the Investigator's judgment or, if appropriate, as indicated by a response of

"yes" since the last visit to question 4 or 5 in the suicidal section, or any response in the behavioral section of the C-SSRS.

16. Subject has a need for use of a live vaccine within 10 weeks of final anticipated dose of IMP for the long-term extension study.
17. Concomitant use of prohibited medications or use of commercially available or investigational biologic therapies (other than tildrakizumab) for PsO and/or PsA (see [Section 10.6](#)).

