### **11.1.1.3 Adverse Events of Special Interest**

The events of severe infections (defined as any infection meeting the regulatory definition of a SAE or requiring intravenous antibiotics whether or not reported as a serious event), malignancies (including non-melanoma and melanoma skin cancer), confirmed Major Adverse Cardiovascular Events (MACE), and drug-related hypersensitivity reactions) will each be

identified a priori as an AE of special interest (AESI) for summarizing in this study. Major Adverse Cardiovascular Events include non-fatal stroke, non-fatal myocardial infarction, and cardiovascular death. All MACE events will be evaluated and adjudicated by a CAC ([Section 12.3.4](#)). An AESI must be reported as if it were an SAE ([Section 11.1.2](#))

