## 8.7 Safety analyses

Safety analyses will be conducted on the ASaT population and will be performed for all safety variables specified below.

The subjects will be summarized based on the actual treatment received at the beginning of the extension study.

The safety analyses of changes from baseline to a specific time point in safety variables (e.g., laboratory parameters, vital signs, and ECG) will only include subjects from ASaT who have data available for both the baseline and the time point under consideration unless otherwise specified. Where relevant, temporal relationships to parent study baseline will be described.

No statistical tests will be performed.

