## **Adverse Events of Special Interest (AESIs)**

The events of severe infections, malignancies (including non-melanoma and melanoma skin cancer, excluding carcinoma in situ of the cervix), confirmed Major Adverse Cardiac Events (MACE), and drug-related hypersensitivity reactions will be identified a priori as AESIs for summarizing in this study. Severe infections are defined as any infection meeting the regulatory definition of a SAE, or any infection requiring IV antibiotics whether or not reported as a serious event, as per the regulatory definition. Major Adverse Cardiac Events include non-fatal stroke, non-fatal myocardial infarction and cardiovascular death. All MACE events will be evaluated and adjudicated by a Clinical Adjudication Committee. The AESIs will be summarized by SOC, PT and treatment group.

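### SAP 8.7.1 plans no AE or AESI rate by exposure interval, so the final AE tables of this long-term safety study cannot separate early from late risk

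*SAP*

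**What the plan says.** The objective in Protocol 8.1 and SAP 2.1 opens "To assess the long-term safety of tildrakizumab when administered to PsA subjects by evaluation of", and the first item under it is the incidence and intensity of all AEs. Protocol 9.2 says the design allows safety to be evaluated at every measured time point after the parent study. Protocol 12.2 says all endpoints will be presented at the Table 9-1 time points, and Protocol 12.2.3 lists AEs and AESIs among the safety data.

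The SAP's AE plan is as follows:

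- **Rate (8.7.1):** "the exposure-adjusted AE incidence rate (per 100 subject-years) will be summarized by treatment group". No time interval is named.
- **Counts (8.7.1):** for repeated events, "the subject will only be counted once at the preferred terminology level in adverse event frequency tables", and likewise per system organ class, over the whole study.
- **AESIs (8.7.1):** "The AESIs will be summarized by SOC, PT and treatment group". Neither a rate nor a time split is named.
- **Grouping (8.7):** "The subjects will be summarized based on the actual treatment received at the beginning of the extension study".

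SAP 8.5.1 does bin exposure by time, including 1-2, 2-3 and more than 3 years, but only to describe exposure. Laboratory values, vital signs, physical examination, ECG and C-SSRS are summarized by visit or assessment time (SAP 8.7.2 to 8.7.6).

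The cohort is selected. Protocol 9.3.1 requires completion of parent treatment and ACR20 at Week 52, "AND the subject has received sufficient clinical benefit, in the opinion of the Investigator, to support continued treatment with tildrakizumab". Protocol 9.3.2 excludes some recent serious infections and active or most past malignancy. It also excludes on this ground: "Subject had myocardial infarction, unstable angina pectoris, or ischemic stroke within the past 6 months prior to the first IMP dose".

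**The concern.** A four-year extension adds follow-up late enough to show harms that emerge or accumulate with time. Malignancy, MACE and severe infection are already named as AESIs. A rate taken over the whole extension averages early and late person-time, so a late rise is diluted and a fall is hidden. AEs and AESIs lead the primary objective, yet they are the safety data that the SAP does not show over time. If interval cuts are chosen only after the data are seen, they will carry less weight than cuts fixed beforehand.

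**Working it through.** **No figure to reproduce.** The documents give no planned AE rate, event count or power. The sample size is whoever rolls over (SAP 5), and no tests are planned (SAP 8.7). The arithmetic below is therefore illustrative.

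**Inputs from the documents.** Up to 286 entrants (Protocol 9.1.1, SAP 3.1); maximum duration 208 weeks (SAP 3.3); last dose at Week 200 (Protocol 9.1.3.1.2); exposure is last dose date minus first dose date plus 1 day (SAP 8.5.1).

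**Assumptions.** Constant dropout d per year of 5% to 20%, and the yearly event rates used below.

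**1. Dilution of a late rise.** Hazard h = -ln(1-d). Person-years in year i = 286 × (exp(-h(i-1)) - exp(-h·i)) / h. If the rate doubles in year 4 only, pooled rate ratio = 1 + year 4 share. If it doubles in years 3 and 4, the ratio = 1 + the sum of both shares.

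| Dropout per year | Person-years, years 1/2/3/4 | Total | Year 4 share | Ratio, year 4 doubles | Ratio, years 3 and 4 double |
|---|---|---|---|---|---|
| 5% | 279/265/252/239 | 1,034 | 23% | 1.23 | 1.47 |
| 10% | 271/244/220/198 | 934 | 21% | 1.21 | 1.45 |
| 15% | 264/224/191/162 | 841 | 19% | 1.19 | 1.42 |
| 20% | 256/205/164/131 | 757 | 17% | 1.17 | 1.39 |

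If person-time stops at the Week 200 dose, as in SAP 8.5.1, maximum exposure is 200 × 7 + 1 = 1,401 days (3.84 years). At 10% dropout, year 4 then supplies 166 of 902 subject-years (18%), so the dilution is slightly greater.

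**2. Different time patterns, same planned figure.** With 10% dropout and follow-up to Week 200, subject-years are 271/244/220/166. Three patterns, each scaled to a pooled 2.0 per 100 subject-years, have these yearly rates:

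- flat: 2.0/2.0/2.0/2.0
- rising fourfold: 0.87/1.73/2.60/3.46
- falling fourfold: 2.98/2.23/1.49/0.74

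Check for the rising case: expected events 2.3 + 4.2 + 5.7 + 5.8 = 18.0, and 100 × 18.0/902 = 2.0. The planned table would show 2.0 in all three cases.

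**3. What interval rates could show.** At 2 per 100 subject-years and 0% to 20% dropout, 1,096 to 737 subject-years give about 22 to 15 events in all. A doubling after year 1 (1.18 to 2.35 at 10% dropout) would have exact 95% CIs of 0.23-3.23 and 1.33-3.92. An exact conditional test would detect it with about 14-15% power. At an assumed 30 per 100 subject-years, as for common TEAEs, the intervals separate (13.0-23.4 against 30.9-40.3) and power exceeds 99%.

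**The case against.** The strongest reply is that the stated objective is incidence and intensity of AEs, and that a descriptive rate from an uncontrolled, untested rollover study meets it. Change of risk with duration is not a named objective. That is correct, so the SAP does not contradict its objective. The narrower point stands: the word is long-term, Protocol 12.2 promises endpoints by time point, and SAP section 10 records no departure from the protocol.

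A reader might infer that the plan as a whole cannot show change over time. It can in part. The other safety variables are shown by visit. All AEs are listed individually, and a safety interim is planned at about one year (Protocol 12.3.3, SAP 8.9). That interim is not a clean year 1 rate, because it waits for the last subject's Week 52 and earlier entrants will have longer follow-up. Table templates are in a separate document that is not available here.

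A reader might also infer that the entry criteria remove most subjects who had an AESI in the parent year, so that early rates start low. The documents do not support this. The serious infection window is 8 weeks and has a further condition on the timing of the last dose. The cardiovascular window is 6 months. Cured basal and squamous cell carcinoma are exempt. Nor is the pooled rate dominated by the early period: in the table above, year 1 supplies 27% to 34% of person-years.

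Two limits on the remedy also stand. Rare AESIs will be sparse: 18 events spread over three groups and four years is 1.5 per cell. Early-against-late contrasts will also reflect the switch to open-label 100 mg Q12W, the move from 4-weekly to less frequent visits, and attrition. These are reasons to present interval rates for all subjects combined and with caveats. They are not reasons to omit them.

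**Conclusion.** The point holds for AE and AESI tables only. As written, SAP 8.7.1 pools rates and counts over up to 208 weeks by starting regimen, and the resulting tables cannot tell early from late risk. A doubling in year 4 would move the pooled rate by about 23% to 17%, and a doubling in years 3 and 4 by about 47% to 39%. These sizes assume the maximum 286 entrants, constant dropout of 5% to 20% per year, four full years of person-time and otherwise constant rates. None of the dropout or event rates comes from the documents. That the pooled figure carries no information on time pattern does not depend on those values. The evidence does not support a claim that interval tables would detect a late doubling of rare AESIs. Their gain there is description, and for common TEAEs it is a usable comparison.

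**What to change.** In SAP 8.7.1, next to the overall rate, add exposure-adjusted rates with 95% CIs for any TEAE, serious TEAEs and each AESI category by extension year: Weeks 0-52, >52-104, >104-156 and >156-208. Present them for all subjects combined as well as by group, with subjects and person-years at risk in each interval. State the person-time rule, including whether follow-up stops at the first event.

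State with the tables that:

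- AESI interval rates are descriptive because counts will be small;
- early-against-late contrasts also reflect the switch to open-label 100 mg Q12W, less frequent visits and attrition;
- results apply to Week 52 ACR20 responders who passed the re-applied exclusions.

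Do not add a cumulative rate that brings in parent-study person-time of entrants only. That time is conditioned on completing, responding and passing the event exclusions, which would tend to lower the rate. It would also need parent-study AE data, because AEs that began in the parent study go on the medical history form here.

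The cost is SAP wording and a few tables from onset and dosing dates already collected. The downside is sparse later intervals.
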